---

Non-invasive Brain Stimulation to Improve Quadriceps Muscle Function After Anterior Cruciate Ligament Reconstruction

NCT #: ID not assigned yet

5/28/20

---

Please fill in all parts of this form that are required. Provide a non-scientific or lay summary of the project that must include the items listed below. The Protocol Summary will be reviewed only if all required sections are completed. **(The spaces provided will expand as you type and will become scroll boxes).** *NOTE: If the protocol is part of a grant, please upload the grant documents (proposal and budget) to the IRBNet package as an appendix.*

**1. Background and Objectives - Describe the purpose of the study. Describe any past studies that are related to this study (short literature review).**

*Quadriceps muscle dysfunction persists for years after anterior cruciate ligament reconstruction (ACLR). Restoring quadriceps function after ACLR is critical as quadriceps performance is related to better self-reported function, reduced risk of reinjury, and better movement patterns. Emerging evidence suggests that alterations in corticospinal excitability (CSE) persist after ACLR, and these alterations are related to poor quadriceps performance (i.e. less strength and slower rate of torque development (RTD)). However, few studies have evaluated quadriceps performance and CSE prior to 6 months after ACLR. Comprehensive evaluation of quadriceps performance and CSE early after ACLR is critical to developing new interventions to mitigate persistent quadriceps dysfunction and improve outcomes.*

*My previous work indicates that after ACLR patients demonstrate alterations in CSE as early as 2 weeks after surgery, and these alterations do not change during the course of post-operative rehabilitation ([name], in review, JOR; [name], in review, JOSPT). More specifically, patients after ACLR demonstrated reduced thresholds and altered excitability, which suggests that the corticospinal tract has a higher recruitment threshold with potentially steep activation curves. Reduced thresholds and steeper recruitment curves may limit a more graded activation of the quadriceps necessary for functional movement and stability. The fact that the alterations in CSE did not change from 2 weeks after surgery to a mean of 4.5 months after surgery suggests that current rehabilitation strategies are not addressing alterations in CSE. There is a need to investigate new neuromodulatory interventions, such as transcranial direct current stimulation, that have the potential to modify CSE and muscle performance in patients after ACLR.*

*Transcranial direct current stimulation (tDCS) increases short-term CSE and isometric strength in healthy participants and stroke survivors. In the proposed pilot study, tDCS will be used as an intervention to determine its effects on CSE and quadriceps muscle performance in patients recovering from ACLR. We will incorporate two measures of quadriceps performance, isometric strength and rate of torque development (RTD) as both measures are altered and related to functional outcomes after ACLR. However, to the best of my knowledge, no studies have determined the effectiveness of tDCS on CSE and quadriceps performance in patients after ACLR, and no studies to date have evaluated the relationship between multiple measures of quadriceps performance and CSE in patients after ACLR. Evaluating new interventions with potential to mitigate alterations in CSE (i.e. active motor thresholds (AMT) and slope of the recruitment curve (SLOPE)) and quadriceps muscle performance (i.e. isometric strength and RTD) in patients recovering from ACLR are critical to improving outcomes in this population. Therefore, the aims of this study are to:*

**Aim 1:** Determine the effects of a single session of tDCS on two measures of CSE and two measures of quadriceps performance in patients after ACLR.

*Hypothesis 2.1: Patients after ACLR will demonstrate increased CSE (lower AMTs and steeper SLOPEs) after one session of active tDCS and no changes in CSE after placebo tDCS.*

*Hypothesis 2.2: Patients after ACLR will demonstrate greater RTD/isometric strength after one session of active tDCS and no changes in RTD/isometric strength after placebo tDCS.*

**Aim 2:** Determine the relationship between two measures of CSE and two measures of quadriceps muscle performance in patients after ACLR.

*Hypothesis 1.1: Greater CSE will be associated with greater quadriceps isometric strength and greater RTD.*

*Hypothesis 1.2: The correlation between CSE and RTD will be greater than the correlation between CSE and isometric strength.*

*Current outcomes following ACLR are less than optimal with patients demonstrating chronic quadriceps dysfunction related to altered movement patterns and the development of post-traumatic knee OA. Emerging evidence suggests that quadriceps dysfunction after ACLR is related to alterations in CSE. Therefore, interventions targeting CSE have the*

*potential to mitigate chronic quadriceps dysfunction, improve movement patterns, and improve outcomes. The proposed study is a logical and essential first step in determining the effect of tDCS, an intervention known to induce changes in excitability, on CSE and quadriceps performance in patients after ACLR. Upon completion of this study, I will have obtained the pilot data needed to apply for a larger grant to investigate the effects of multiple sessions of tDCS on CSE and quadriceps muscle performance, generating the evidence needed to introduce this intervention into the clinical practice.*

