**Anticipated date of Submission:**

**b) Is this a collaboration with another institution (if yes, please move to section 3 c)?**

- Yes
- No

**c) Is each institution doing their own review or will one institution serve as the primary IRB through an Authorization Agreement?**

- Each institution will complete their own review.
- An Authorization Agreement will be signed.

**4. Study Population - Are the human subjects involved in the proposed activity included in the following categories? (check all that apply, at least one box must be checked)**

*Yes. Human subjects are included in this study.*

 Minors	 Pregnant women, human fetuses, neonates
 Prisoners	 AIDS/HIV-positive subjects
 Terminally ill subjects	 Subjects with intellectual disabilities
 Economically and/or educationally disadvantaged persons	 Minorities
 None of the above	 Other Click here to enter text.

**5. Inclusion and Exclusion Criteria - Describe the criteria that define who will be included or excluded in your study sample. If you are conducting data analysis only describe what is included in the data set you propose to use.**

*ACLR Group: Individuals between the ages of 13 and 55 years with a history of ACLR (4 months to 5 years) will be recruited.*

*Uninjured Group: Individuals between the ages of 13 and 55 years without a history of major knee injury or surgery will be recruited for the uninjured group. These participants will be matched to participants in the ACLR group by sex, age, and activity level.*

*Both groups must participate (or participated in prior to surgery) in sports involving jumping, pivoting, cutting on a regular basis to be included. Individuals < 18 years of age will only complete strength testing and questionnaires at one testing session. They will not participate in TMS testing or the intervention (tDCS with stationary bike riding).*

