**Data Analysis**

Independent t-tests will be used to examine demographic differences between the two groups. A 2 (limb) x 2 (group) ANOVA will be used to evaluate differences in strength, TMS, and fNIRS measures. Regression analyses will be used to determine the relationship between the CNS measures and quadriceps strength, and the relationship between the TMS and fNIRS measures.

**9. Compensation or Credit - Describe the amount and timing of any compensation or credit to participants. Identify the source of the funds to compensate participants**

*Each participant (≥18 years of age) will be paid \$100 for their participation in this study. Participants must complete both sessions to receive the compensation.*

*Each participant (<18 years of age) will receive \$50 for their participation in this study as they will only complete one session.*

**10. Risk to Participants - List the reasonably foreseeable risks, discomforts, or inconveniences related to participation in the research. Consider physical, psychological, social, legal, and economic risks.**

*Risks associated with Testing Procedures (TMS, strength testing)*

*There are no known long term risks of TMS. There is a very small risk of seizure, syncope, and change in auditory thresholds. A recent study examining adverse events of TMS concluded: "Our data suggest that single/paired-pulse and repetitive TMS, conducted within the published guidelines pose a very small increment over the background risks of everyday life to subjects without known risk factors." Screening potential participants for a prior history of seizures, syncope, and hearing impairments will allow us to exclude individuals at increased risk. Participants will be offered ear plugs if the sound from the TMS pulse is uncomfortable.*

*In the very unlikely event of a seizure, the following steps will be taken: 1) The participant will be positioned in the safest position to maintain an open airway (i.e. laying supine or side lying), 2) emergency personal will be contacted by dialing 911 (research assistant), 3) any objects will be moved away from the participant to prevent additional injury, 4) monitor vitals until emergency personal arrive.*

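### Does predicting a steeper recruitment curve after active tDCS contradict the protocol's own account of what is wrong after ACLR?

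*Protocol*

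**What the plan says.** All the relevant text on direction is in section 1 (Background and Objectives) of the protocol. The hypotheses under Aim 1 are numbered 2.1 and 2.2, and those under Aim 2 are numbered 1.1 and 1.2.

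- **Observed state after ACLR.** The investigator's previous work is said to show reduced thresholds and altered excitability, "which suggests that the corticospinal tract has a higher recruitment threshold with potentially steep activation curves".
- **Possible consequence.** "Reduced thresholds and steeper recruitment curves may limit a more graded activation of the quadriceps necessary for functional movement and stability".
- **Reason for the study.** "Evaluating new interventions with potential to mitigate alterations in CSE (i.e. active motor thresholds (AMT) and slope of the recruitment curve (SLOPE" is given as critical to better outcomes.
- **Link to performance.** The opening paragraph says of the CSE alterations that "these alterations are related to poor quadriceps performance (i.e. less strength and slower rate of torque development (RTD", without giving them a direction.
- **Hypothesis 2.1.** "Patients after ACLR will demonstrate increased CSE (lower AMTs and steeper SLOPEs) after one session of active tDCS", with no change after placebo.
- **Hypothesis 2.2.** Greater RTD and isometric strength after active tDCS, with no change after placebo.
- **Hypothesis 1.1.** "Greater CSE will be associated with greater quadriceps isometric strength and greater RTD".

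The only analysis stated for group differences, in the Data Analysis part of section 8, is: "A 2 (limb) x 2 (group) ANOVA will be used to evaluate differences in strength, TMS, and fNIRS measures".

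**The concern.** Taken at face value, the background treats a steep curve as part of the problem, the study looks for something to mitigate the problem, and the hypothesis predicts a steeper curve. A steeper SLOPE after active tDCS would then confirm Hypothesis 2.1 and also reproduce the pattern described as possibly limiting. A flatter SLOPE would fail the hypothesis yet fit mitigation.

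AMT is harder still. One sentence has thresholds both reduced and higher, so a lower AMT could be read as correcting the alteration or adding to it.

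Hypothesis 1.1 seems to share the difficulty. The alterations are tied to weaker and slower contraction, while greater CSE, which Hypothesis 2.1 defines as including a steeper SLOPE, is expected to go with stronger and faster contraction.

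At stake is interpretation. If no reading of an AMT or SLOPE change is fixed in advance, one could be picked once the results are known, and section 1 says these pilot data are to support an application for a larger study.

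**Working it through.** The protocol gives no figure on this point, so the check sets the statements side by side and asks what in the plan depends on them.

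**1. Direction, outcome by outcome (Aim 1)**

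| Outcome | Background: state after ACLR | Predicted after active tDCS | Relation |
|---|---|---|---|
| SLOPE | steep, qualified as potential | steeper | in tension |
| AMT | both reduced and higher | lower | cannot be placed |
| Isometric strength | less | greater | consistent |
| RTD | slower | greater | consistent |

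So 1 of 4 outcomes is in tension, 1 of 4 is undetermined, and 2 of 4 agree.

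**2. How firm the SLOPE premise is.** The reported observation is altered excitability, with no direction. Steepness enters as something the data suggest, is called potential, and has a consequence that may follow. It also shares its sentence with the threshold statement that contradicts the line before. A premise hedged three times does not support the conclusion that a steeper SLOPE could never be read favourably.

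**3. What Hypothesis 2.1 asserts.** Aim 1 is to determine the effects of one session. The predicted direction follows from studies cited in the same section, in healthy people and stroke survivors, where tDCS raised CSE for a short time and raised isometric strength. Hypothesis 2.1 says active tDCS will do the same here. It does not call the change a benefit, and the protocol sets no mitigation criterion for AMT or SLOPE. The mitigation phrase applied to AMT and SLOPE stands in one background sentence.

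**4. What would change if the direction of the deficit were settled.**
- Measurement: AMT is the stimulator output giving at least 5 of 10 responses above 100 µV, and the curve uses intensities from 80% to 140% of AMT. Neither depends on which direction is the deficit.
- Test: the named methods are t-tests, an ANOVA and regressions. The ANOVA F-test has no direction, and a regression coefficient carries its own sign.
- Estimates and numbers recruited: unchanged.

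**5. How results would read under the hypotheses as written.**

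| SLOPE after active tDCS | Strength and RTD | Reading |
|---|---|---|
| steeper | better | 2.1 and 2.2 supported for these outcomes |
| steeper | not better | CSE raised, no performance gain shown |
| not steeper | better | performance gain without the predicted SLOPE change |
| not steeper | not better | neither supported for these outcomes |

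Each row can be reported without first deciding whether steep is the deficit.

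**6. Aim 2.** The opening paragraph gives the alterations no direction, so a conflict with Hypothesis 1.1 has to borrow the hedged steepness remark. That remark concerns graded activation for movement and stability, whereas Hypothesis 1.1 concerns maximal isometric strength and RTD. Hypothesis 1.1 is also the very association under test, and either sign can be reported.

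**The case for a change.** The strongest case for a change is that the protocol contains both statements, reconciles them nowhere, and could do so cheaply. Hypothesis 1.1 cannot supply the missing premise, because it is itself under test. That tDCS raises CSE in healthy people does not make a steeper curve a correction in patients whose curves may already be steep.

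This stands as far as it goes. The text is inconsistent, and a SLOPE change in the predicted direction would not by itself show mitigation.

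The step from there to a changed plan is what fails. Recasting Hypothesis 2.1 as a question about mechanism, and resting functional benefit on strength and RTD, largely restates Aim 1 and Hypothesis 2.2. Rewording the background or Hypothesis 1.1 alters nothing that is measured or tested.

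The one substantive option would allow a mitigation claim only when the tDCS effect runs opposite to the baseline ACLR-minus-uninjured difference, and only when that difference excludes zero. It has three weaknesses:

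- **Precision.** In SD units, the 95% half-width for two independent means is t(0.975, 2n−2) × √(2/n). At n = 30 per group (section 6) it is 2.00 × 0.258 = 0.52. Under-18s are recruited, but "They will not participate in TMS testing or the intervention (tDCS with stationary bike riding"; their number is not given. If only 15 per group are adults, an assumption, it is 2.05 × 0.365 = 0.75. Both figures ignore the matching and the limb factor. They describe the proposed rule, not any harm from the present wording.
- **Definition.** TMS covers both hemispheres, two tasks and two sessions. The limb-by-group ANOVA is not said to use pre-stimulation data, so the baseline would have to be newly defined.
- **Value.** It would guard a mitigation claim for which the protocol sets no criterion, and would give up a directional prediction made in advance.

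**Conclusion.** No change to the plan follows. The mismatch is real but is confined to explanatory background in a form that asks for a lay summary, written for a pilot study. It touches the interpretation of SLOPE and, through a sentence that contradicts itself, of AMT. It leaves strength and RTD alone and alters no measurement, contrast, test, estimate or sample size.

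The predicted directions are stated in advance, so confirmation of Hypothesis 2.1 cannot be redefined afterwards. Only the functional meaning of a CSE change is open, and Hypothesis 2.2 and Aim 2 are there to inform it. An analyst would report a change in the predicted direction as increased CSE and would not call it mitigation or benefit on that evidence alone.

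This rests on two readings: that Hypothesis 2.1 is a mechanistic prediction, and that CSE changes will be tested without a one-sided rule, since the protocol names none. The investigator's earlier work, which might settle the direction of the alteration, is not available here, and the conclusion does not depend on it.

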**2. Data Use (Select all that apply):**

- Dissertation, Thesis, Undergraduate honors project
- Publication/journal article, conferences/presentations
- Results released to agency or organization
- Results released to participants/parents
- Results released to employer or school
- Other [Click here to enter text.](#)

**3. External IRB:**

**a) Is this proposal currently under review or has it been reviewed and approved by another institution's IRB?** IF YES, include a copy of the proposal and if available, IRB approval from that institution. If the proposal has not yet been submitted to the other institution, please note an anticipated date of submission and a copy of the other institution's review guidelines.

- Yes
- No

**Anticipated date of Submission:**

**b) Is this a collaboration with another institution (if yes, please move to section 3 c)?**

- Yes
- No

**c) Is each institution doing their own review or will one institution serve as the primary IRB through an Authorization Agreement?**

- Each institution will complete their own review.
- An Authorization Agreement will be signed.

**4. Study Population - Are the human subjects involved in the proposed activity included in the following categories? (check all that apply, at least one box must be checked)**

*Yes. Human subjects are included in this study.*

 Minors	 Pregnant women, human fetuses, neonates
 Prisoners	 AIDS/HIV-positive subjects
 Terminally ill subjects	 Subjects with intellectual disabilities
 Economically and/or educationally disadvantaged persons	 Minorities
 None of the above	 Other Click here to enter text.

**5. Inclusion and Exclusion Criteria - Describe the criteria that define who will be included or excluded in your study sample. If you are conducting data analysis only describe what is included in the data set you propose to use.**

*ACLR Group: Individuals between the ages of 13 and 55 years with a history of ACLR (4 months to 5 years) will be recruited.*

*Uninjured Group: Individuals between the ages of 13 and 55 years without a history of major knee injury or surgery will be recruited for the uninjured group. These participants will be matched to participants in the ACLR group by sex, age, and activity level.*

*Both groups must participate (or participated in prior to surgery) in sports involving jumping, pivoting, cutting on a regular basis to be included. Individuals < 18 years of age will only complete strength testing and questionnaires at one testing session. They will not participate in TMS testing or the intervention (tDCS with stationary bike riding).*

*Subjects recruited for either group will also be excluded if: (1) they are currently on anti-epileptic medication or have a history of epilepsy or seizures (2) have a first-degree family member with a history of epilepsy (3) had a prior head injury that required hospitalization or concussion in the past 6 months (4) have any metal in the head, eyes, neck or face (with the exception of dentures) (5) have a history of brain surgery (6) have skull abnormalities or fractures (7) have implantation of electrical devices such as (but not limited to) cardiac pacemaker, cardiac defibrillator, cochlear implants or nerve stimulators (8) history or recurring or severe headaches/migraines (9) known neurological disorders or muscle diseases (10) pregnancy (11) lower extremity botulinum injections in past 6 months (12) baclofen pumps (13) taking any medications that act on the central nervous system. Potential participants will be screened verbally of via email for these exclusion criteria prior to consent. At time of consent, the TMS Adult Safety Screen will completed in writing by each potential participant to again screen for these criteria. Yes answers to questions 1, 3, 5, 6, 7, 8, 9, 10, 12, 13 are absolute exclusions. Yes answers to 2, 4, 11, 14, 15 will trigger follow up questions. Individuals with a chronic history of syncope, ringing in the ears (yes answer to 2, 4) will be excluded. Individuals taking any medications affecting the CNS will be excluded. Individuals with previous adverse reactions to TMS and/or MRI (questions 14, 15) will be excluded.*

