**6. Number of Participants - Indicate the total number of anticipated participants to be recruited and enrolled.**

*Thirty subjects without a history of major knee injury/surgery and 30 subjects with a history of ACLR will be recruited for this study.*

**7. Recruitment Method - Describe who will be doing the recruitment of participants. Describe when, where, and how potential participants will be identified and recruited. Describe and attach materials that will be used to recruit participants (attach documents or recruitment script with the application).**

*The following recruitment methods will be used for this study.*

- a. *Two flyers have been created for recruitment (see attached, one flyer for uninjured participants and one for participants after ACLR). These flyers will be posted on bulletin boards at Arcadia University, posted on social media, emailed to students, and emailed to local physical therapists.*
- b. *Individuals with a history of ACL reconstruction will be recruited from local physical therapy clinics. Physical therapists will be notified of the study via email and/or phone and asked to have interested participants complete the "consent to contact form". Email/phone scripts are below. Good Sheppard/PENN Partners (GSPP) has a physical therapy clinic on campus. GSPP requires that a specific consent to contact form. Therefore, two consent to contact forms will be attached to this protocol. The physical therapists will only be informing the patients or patients guardians (if under 18 years old) that they may be eligible for a study being conducted at Arcadia University and having the patients/guardians complete the consent to contact form. Patients who complete the consent to contact form will be contacted by the PI who will determine eligibility and explain the study in more detail. Only the PI will be gaining consent with each subject.*

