**Strength testing**

Testing will take place in the Exercise Testing Lab (Room 109, Health Sciences Building). Strength testing will consist of maximal voluntary contractions of the quadriceps muscles of both legs. This testing is performed routinely during physical therapy for individuals with knee pathology. Participants will be seated upright in a dynamometer (HUMAC NORM), a device that secures their pelvis and limbs and resists the patient's attempt to straighten the knee from 90 degrees of knee flexion. The participant will be asked to kick as hard as they can against the arm of the dynamometer to calculate their maximum volitional isometric contraction (MVIC). The amount of force/torque produced will then be recorded. Prior to the MVICs, a series of three sub-maximal practice trials will be performed to familiarize each participant with the task. Three MVICs will then be performed and recorded for analysis. Two additional (one warm up and one test set) sets of five repetitions will be performed to test both quadriceps and hamstring strength through the patients full available range of motion.

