**Transcranial direct current stimulation (tDCS)**

a-tDCS (Soterix 1x1, Soterix Medical Inc, NY, NY) will be delivered over the primary motor cortex contralateral to the surgical limb (i.e. hot spot for the vastus medialis muscle representation found during TMS testing). A pair of carbon electrodes placed in saline-soaked sponges (surface area: 5 x 7  $\text{cm}^2$ ) will be secured to the scalp using straps (Soterix EASYstrap). The anode will be centered over the hotspot while the cathode will be placed on the right supraorbital area. a-tDCS will be administered while the participant rides a stationary bike for 20 minutes. The bike seat will be adjusted for each participant so that maximal knee flexion range of motion will be 90 degrees. Participants will also be instructed to maintain a neutral ankle angle. Verbal feedback provided by an investigator will be provided throughout the intervention to maintain the neutral ankle position. The standardized seat position and ankle position is to prevent the participant from using their ankle plantarflexors during the pedaling motion. Stationary bike riding was chosen as this task is commonly performed early after ACLR with minimal stress to the healing graft and requires quadriceps activity. The first 5 minutes will serve as a warmup with the patient maintaining a rate of perceived exertion (RPE) of light or 1 out of 10. Over the next 10 minutes, the resistance will be increased to maintain a RPE of moderate or 3/10. The last 5 minutes will serve as a cool down at the same intensity/resistance as the warm up. Active a-tDCS will be applied at an intensity of 2mA with a 30-second ramp-up and 30-second ramp-down for the entire duration of bike riding, while the sham a-tDCS will be applied for only the first 30 seconds.

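### The ACLR criteria admit people with both ACLs reconstructed or an injured opposite knee, although the stimulation site is set by a single surgical limb and the analysis compares limbs

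*Protocol*

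**What the plan says.** Section 5 (Inclusion and Exclusion Criteria) defines the surgical group in one sentence: "Individuals between the ages of 13 and 55 years with a history of ACLR (4 months to 5 years) will be recruited". It does not mention side, number of reconstructions or the state of the other knee. Section 6 gives the numbers, again without qualification: "Thirty subjects without a history of major knee injury/surgery and 30 subjects with a history of ACLR will be recruited for this study".

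The uninjured group is held to a knee standard, namely people "without a history of major knee injury or surgery will be recruited for the uninjured group". That clause is not applied to the opposite knee of ACLR participants.

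The exclusions common to both groups begin "Subjects recruited for either group will also be excluded if: (1) they are currently on anti-epileptic medication or have a history of epilepsy or seizures" and run to 13 items. They cover seizure risk, head injury and metal, implants, headache, neurological and muscle disease, pregnancy, botulinum, baclofen pumps and medication. None concerns the knee.

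Three parts of Section 8 depend on limb:

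- tDCS: stimulation "will be delivered over the primary motor cortex contralateral to the surgical limb".
- Strength testing: "Strength testing will consist of maximal voluntary contractions of the quadriceps muscles of both legs". TMS is likewise done for both hemispheres.
- Data Analysis: "A 2 (limb) x 2 (group) ANOVA will be used to evaluate differences in strength, TMS, and fNIRS measures". The two limb levels are not defined.

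**The concern.** Who may enter the ACLR group does not match what the procedures and analysis need from its members. The stimulation rule identifies a hemisphere only if there is exactly one operated knee. The limb factor gives an informative contrast in the ACLR group only if the opposite knee is a reasonable comparison.

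The gap could plausibly be met in practice. Participants must take part, or have taken part before surgery, in jumping, pivoting or cutting sports. The window reaches back 5 years, and recruitment is by flyers, social media and physical therapy clinics.

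Two things are at stake. For an adult with both ACLs reconstructed, the stimulated hemisphere and the limb coding would have to be chosen ad hoc. For anyone whose opposite knee is also impaired, the within-person limb difference tends to be smaller, which pulls the group's limb contrast toward zero.

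**Working it through.** **Step 1. Compare each type of participant with the two limb-dependent rules.** All three types below satisfy Section 5 as written, provided an ACLR falls inside the window.

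| Participant | Is the surgical limb, and so the hemisphere, defined? | Is the limb contrast sound? |
|---|---|---|
| Both ACLs reconstructed | No, there are two | No non-surgical limb exists |
| One ACLR, opposite knee injured but not operated | Yes | Comparison limb compromised |
| Revision on the same knee | Yes | Yes, but which operation starts the 4-month to 5-year window is unclear |

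Surgery other than ACLR on the opposite knee also compromises the comparison limb.

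**Step 2. Size of the shrinkage.** The protocol gives no power calculation, effect size, SD or alpha, so there is no stated figure to reproduce. Let d be the mean limb difference in ACLR participants with an unaffected opposite knee. Let p be the share with an affected opposite knee, and r the fraction of d that they still show.

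Mean contrast = (1 - p)d + p·r·d = (1 - p + p·r)d

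With equal deficits in both knees, r = 0 and the factor is 1 - p:

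- p = 0.05 (1.5 of 30): 0.95
- p = 0.10 (3 of 30): 0.90
- p = 0.20 (6 of 30): 0.80

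With r = 0.5 and p = 0.10, the factor is 1 - 0.10 + 0.05 = 0.95. So 1 - p is the low end as long as the opposite knee is not the worse of the two. Both p and r are assumptions.

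**Step 3. What this could mean for power (illustration only).** The limb-by-group interaction is equivalent to comparing within-person limb differences between two groups of 30. Assume two-sided alpha 0.05, an SD of 1 for the limb difference, no expected limb difference in controls, and r = 0. The mixture adds p(1 - p)d² to the ACLR variance.

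For d = 0.75 and p = 0.10:

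- Mean = 0.90 × 0.75 = 0.675
- ACLR variance = 1 + 0.09 × 0.5625 = 1.051
- Averaged SD = √((1 + 1.051)/2) = 1.013
- Power = Φ(0.675/(1.013 × √(2/30)) - 1.96) = Φ(0.62) = 73%

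| d (in SD) | p = 0 | p = 0.10 | p = 0.20 |
|---|---|---|---|
| 0.50 | 49% | 41% | 34% |
| 0.75 | 83% | 73% | 62% |
| 1.00 | 97% | 93% | 85% |

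At d = 0.75, the number per group for 80% power would be 28, 36 and 46 respectively. Thirty per group is the most favourable case for TMS and fNIRS, because participants under 18 complete only strength testing and questionnaires.

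**Step 4. Same-knee revision.** If 10% of the group had a revision on the same knee, with a deficit equal to d or 1.5 times d, the mean contrast at d = 0.75 would be 0.75 to 0.788 and power 83% to 86%. There is no dilution.

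**Step 5. Which analyses are affected.** Aim 1 concerns change after active versus placebo tDCS. Aim 2 concerns the association of corticospinal excitability with quadriceps performance. No hypothesis under either aim is a between-limb comparison, so the shrinkage bears on the ANOVA alone.

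**The case against.** The best reply has four parts.

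- **Intent.** The stimulation rule speaks of the surgical limb in the singular, which suggests that unilateral cases were intended. The principal investigator alone determines eligibility and obtains consent, so inconsistent reading across recruiters is unlikely. This is fair, but the written criteria give that one person no rule to apply to a bilateral case.
- **Limb coding.** Defining the limb levels can be left to an analysis plan, and the levels are equally undefined for the 30 controls, who have no surgical limb. This stands as far as coding goes. Eligibility and the choice of hemisphere are different: they are settled at enrolment and treatment, and an analysis plan cannot repair them.
- **Size.** The factor 1 - p restates its own assumption. The protocol gives no p, and two knees injured or operated at different times need not have equal deficits. This stands. A reader might take 5% to 20% as an estimate of bias, but it is only what follows from assumed shares and a zero limb difference.
- **Reach.** A reader might infer that the main aims are undermined. They are not, because neither aim tests a limb contrast. What remains for Aim 1 is an unspecified hemisphere for an unknown, possibly zero, number of adults; minors receive no tDCS.

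A reader might also infer that revision ACLR makes the limb factor meaningless, or that the group should be limited to primary reconstructions. The protocol supports neither. A same-knee revision leaves one surgical limb, one target hemisphere and a usable contrast.

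**Conclusion.** The point holds, within limits. Section 5 admits participants for whom the stimulation rule names no hemisphere (bilateral ACLR) or for whom the comparison limb is not sound (bilateral ACLR, or major injury or surgery of the opposite knee). The first problem arises with a single bilateral adult, whatever p is.

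The second would tend to shrink the limb-by-group contrast, to a factor of 1 - p under equal deficits in both knees and by less if the operated knee remains the worse. The actual size cannot be derived from the protocol. The power figures rest on assumed effect sizes, shares, SD and alpha. The effect is confined to the ANOVA. For same-knee revision the only defect is the undefined start of the time window.

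This is a cheap improvement to make before enrolment, not a flaw that defeats the study.

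**What to change.** In Section 5, limit the ACLR group to unilateral ACLR with no major injury or surgery of the opposite knee. This extends to the comparison limb the standard already set for the uninjured group.

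If the investigator prefers to keep such participants, define in advance how the index limb is identified and leave them out of the between-limb comparison.

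In either case, state which operation the 4-month to 5-year window counts from when there has been a revision. Excluding revisions is not needed.

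The change takes a line or two in the eligibility section and one added screening question. The downside is a slightly smaller recruitment pool.
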